### **3.2. Study Milestones and Time Line**

The trial will include a 9-month start-up phase to include the development of an EDC and operational tools, IRB approval, and initial meetings of study committees (eg. Patient Advisory Board, Steering Committee). The recruitment phase will include the enrollment of approximately 20,000 participants and a 6-month follow up period, and involve the collection of clinical and patient-reported data at enrollment, the perioperative period, and at 1-, 3-, and 6-months post-surgery. This phase will be followed by data analysis and the production of the final report/manuscript.

## **4. Protection of Human Subjects**

### **4.1. Risks to the Subjects**

#### **4.1.1. Human Subjects Involvement and Characteristics**

All patients 21 years of age or older who elect to undergo total hip or knee replacement as treatment of end-stage arthritic disease will be eligible for recruitment and enrollment.

The characteristics of the subject population will reflect the characteristics of the general population undergoing total joint replacement; ages will range from mid-30s to mid-80s, and of a general health status that would allow medical clearance for an elective major orthopaedic surgical procedure. We anticipate enrollment of approximately 25,000 patients. Consecutive patients of participating surgeons at a goal of 25 selected institutions under the direction of the field site PI will be recruited and asked to consider enrollment in the study, as noted previously in section 3.1.2a. Recruitment and retention benefits to the subjects include enhanced awareness of prevention, diagnosis, and treatment of standard thromboembolic complications of total joint replacement procedures. Stratified randomization will occur for patients who have a medical contraindication to use of any one or two of the three study prophylaxis regimens for venous thromboembolism employed in the trial as well as for patients at those sites using a restricted randomization scheme due to fixed structural barriers. Exclusion criteria include a preoperative need for chronic anticoagulation other than with antiplatelet medications, a known condition of thrombophilia proven by diagnostic laboratory testing, or any of the criteria previously stipulated in section 3.1.2 (c). No prisoners or other vulnerable patient populations will be included in the study.

It is anticipated that gender of the study participants will reflect that of the general population with arthritic disease, having a slight predilection for women over men by approximately 55% to 45%. Racial and ethnic diversity will reflect the location and socioeconomic nature of the participating sites, a majority of which are urban academic health centers. This fact ensures the quality of the clinical trial infrastructure as well as a balance of urban and rural locations that will preferentially include under-represented racial and ethnic minorities served by these safety net institutions.

A concealed centralized randomization schedule will provide assignment to one of the prophylaxis regimens, as specified in section 3.1.2b, in randomly varying block sizes of 3, 6, and 9 developed separately for each clinical site and stratified according to type of surgery (hip or knee replacement).

### **Targeted/Planned Enrollment Table**

Source of these data is the 2012 National Inpatient Sample for total hip and knee replacement procedures performed in the United States. The prevalence of TKA is roughly 2x that of THA in the United States, so these tables are weighted in such a way that TKA is expected to contribute twice as many patients as THA to the aggregate sample for PEPPER. The relative racial/ethnic/gender data are applied for each procedure in the joint specific table in a ratio of 1:1 for TKA:THA and then added together in the third table to provide overall projections for the study.

**Total Planned Enrollment: 20,000****TOTAL HIP REPLACEMENT (1/3 of total 20,000 sample)**

Race	Male (N)	Female (N)	Total (N)
American Indian/Alaska Native	8	10	18
Asian	19	31	50
Black/African American	180	240	420
Hawaiian/Pacific Islander			
White	2746	3299	6046
Multirace	64	70	134
Ethnicity	Male (N)	Female (N)	Total (N)
Hispanic (Latino/Latina)	86	100	186
Non-Hispanic	2930	3550	6480

**TOTAL KNEE REPLACEMENT (2/3 of total 20,000 sample)**

Race	Male (N)	Female (N)	Total (N)
American Indian/Alaska Native	21	38	59
Asian	50	117	166
Black/African American	246	742	987
Hawaiian/Pacific Islander			
White	4496	7320	11816
Multirace	104	200	304
Ethnicity	Male (N)	Female (N)	Total (N)
Hispanic (Latino/Latina)	240	447	687
Non-Hispanic	4678	7969	12646

**AGGREGATE SAMPLE – THA and TKA for PEPPER for 20,000**

Race	Male (N)	Female (N)	Total (N)
American Indian/Alaska Native	29	48	77
Asian	53	148	217
Black/African American	426	982	1407
Hawaiian/Pacific Islander			
White	7242	10619	17862
Multirace	168	270	438
Ethnicity	Male (N)	Female (N)	Total (N)
Hispanic (Latino/Latina)	326	547	874
Non-Hispanic	7608	11518	19126

These data from the NIS match very closely with the corresponding data below from the FORCE total joint replacement registry, with whom we will closely work to analyze patient reported functional outcomes as baseline information to compare with the information collected in the PEPPER trial.

Racial Categories FORCE Registry	Ethnic Categories				Total
	Not Hispanic or Latino		Hispanic or Latino		
	Female	Male	Female	Male	
American Indian or Alaska Native	0.58%	0.38%	0%	0%	0.96%
Asian	0.60%	0.38%	0%	0%	0.98%
Native Hawaiian or Other Pacific Islander	0%	0%	0%	0%	0%
Black or African American	3.90%	2.60%	0%	0%	6.50%
White	52.82%	35.22%	1.16%	0.78%	89.98%
More than one race	0.78%	0.54%	0.16%	0.10%	1.58%
	58.68%	39.12%	1.32%	0.88%	100.00%

(Courtesy, [name])

#### 4.1.2. Sources of Materials

Blinded and coded patient information will be obtained at each field site from the hospital chart, specific data collection forms unique to the proposed study, and routine clinic visits in the outpatient record following operation. No tissue specimens or other matter will be removed from the study subject for purposes of the proposed investigation.

Data will be obtained directly from any diagnostic tests performed to establish the presence of pulmonary embolism, symptomatic deep venous thrombosis, or any site of suspected substantial occult bleeding. Individually identifiable private patient information will only be available at the respective field sites at the time of original data collection. Confidentiality of patient identifiers will be protected except as required by law or for regulatory purpose. Thereafter, all data will be entered into web-based databases in coded form, maintained at the respective individual field sites, and securely stored in the central data management center and web-based repository in aggregate. All patient identification will be removed from data at the field site before aggregate reporting.

#### 4.1.3. Potential Risks

Risks to human subjects in this trial include any and all of those typically experienced in the course of “standard of care” treatment and prophylaxis for venous thromboembolism after total hip or knee replacement. There are no experimental drugs or treatment regimens involved in this trial, and so there are no risks associated with any experimental interventions. Likewise, there are no other special risks that are unique to this trial. There are risks associated with randomization since patients will be assigned to a treatment group by chance. One treatment group may prove to be more or less effective or to have more or fewer side effects than the other study treatments or other available treatments. However, each of the three regimens in this trial is commonly used in “standard of care” practice following hip and knee replacement surgery and each has been approved by the FDA and expert guideline groups for use in this manner to prevent venous thromboembolism.

Each of the anticoagulants carries a risk of bleeding, reoperation to evacuate a hematoma from the incision, and secondary infection of the hematoma. Aspirin may cause gastritis and intestinal bleeding may result, or patients may develop an allergy to aspirin that interferes with breathing. Warfarin may accumulate in patients who have liver disease or result in an idiosyncratic reaction with elevation of the INR and may require reversal. Rivaroxaban may accumulate in patients who have kidney disease and may require reversal. Pneumatic compression stockings or foot pumps may be annoying or uncomfortable while wearing them in the hospital. The estimated likelihood of the risks of pulmonary embolism and re-operation for bleeding are as follows:

Medication	Reoperation for Bleeding	Pulmonary Embolism
Aspirin	1 in 500 (0.2%)	1 in 50 (2.0%)
Warfarin	1 in 100 (1.0%)	1 in 100 (1.0%)
Rivaroxaban	1 in 20 (5.0%)	1 in 200 (0.5%)

Serious adverse events (SAE) will be defined as any death or unplanned readmission to the hospital, reoperation or other procedure related to the index operated joint, transfusion, aspiration of the operated joint, or any other event that may be attributed to use of one of the anticoagulant medications central to the clinical trial. SAEs will be considered by the DSMB in their regular reviews and reported to the IRB as appropriate and determined by the DSMB and executive oversight group.

### Confidentiality Risks

All patient data will be coded and concealed for patient identity at the clinical site in which the patient is enrolled in the trial. Upon initial enrollment, each patient's identity will be concealed by assignment of a numeric identifier that will be contained in the master data file as developed by Statix, as the centralized data collection agent. The data coordinating center, in preparation of the DSMB reports, and the executive oversight committee will have access to unblinded data, but patient identities will remain concealed throughout the trial.

Confidentiality will be maintained during all phases of DSMB review and deliberations, and participants in DSMB meetings will maintain strict confidentiality concerning all privileged trial results provided to them. Only results for the entire study population (without regard to treatment group) will be presented during open sessions of the DSMB. Presentation of patient-specific information (e.g., SAE reports) will not include information that would allow the identification of individual participants. Treatment group specific data presented in closed session reports will be labeled Group A, B, or C in case the documents are inadvertently viewed by individuals other than those participating in the closed session. However, at the meeting, DSMB members will be informed of the identity of the groups (aspirin vs. warfarin vs. rivaroxaban). All participants in DSMB meetings will be required to sign a confidentiality statement at the start of every meeting. All materials, discussions and proceedings of the DSMB are completely confidential. Members and other participants in DSMB meetings are expected to maintain confidentiality.

Electronic versions of data and DSMB material will be stored on secure computers with password protection. Paper copies of forms and reports will be kept in locked filing cabinets with access restricted to a small number of Data Coordinating Center staff members. Access to data will be on a strictly need-to-know basis.

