## 3.1.3. Data Analysis

Primary Data Analysis

The unblinded nature of the clinical trial could threaten unbiased comparisons. Randomized patients will not be notified of treatment group assignment until the day of the proposed operation, unless necessary to provide third party insurance coverage for prescribed medical care. Further, our trial is protected from this threat to adherence with treatment assignment by the short course of treatment, the follow-up contact to ascertain treatment, and the motivation of each patient to take prescribed drugs to prevent PE and DVT. The trial is protected from the threat to unbiased outcome ascertainment and classification by the independent centralized contact with patients to determine need for collection of clinical documents, preparation of documents related to readmission or treatment for bleeding or thrombosis to remove any indication of treatment assignment, and blinded outcome classification based upon expert review of the redacted documents by the OAC.

**1.0 Primary Aim 1.** *To compare the frequency of the aggregate clinical endpoint of important venous thromboembolism (clinical PE and DVT leading to hospital readmission) and all-cause mortality.*

**1.1 Risk Estimates.** First, 6-month probabilities of our primary composite endpoint (clinical PE, clinical DVT, and all-cause mortality) by treatment group will be estimated and compared. To address the fact that some participants will have incomplete follow-up (e.g., we may know whether they had an event within 3 months but not for the full 6 months), we will estimate 6-month risk of an event using a Kaplan-Meier approach. Confidence intervals will be based on Greenwood's formula (applied using the delta method to a complementary log-log transformation of the estimated risk). In these calculations, those whose follow-up is incomplete will be censored at the time that the follow-up ends.

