### Missing Data

A high retention rate of enrolled participants is critical to the internal and external validity of a randomized clinical trial. Patients who are more difficult to locate or are less cooperative in follow-up participation generally have lower social and residential stability, poorer treatment outcomes, and are more likely to experience financial, marital

status, and occupational changes. Many of these same factors are also well known to contribute to differences in health outcomes, health disparities, and healthcare utilization differences. To minimize non-response and loss to follow-up bias, we will rely on independent established third party data collectors who will devote considerable levels of charted effort to follow-up data collection. This approach to centralized data collection will ensure serial efforts to obtain follow-up of research subjects through mail, telephone, electronic communication, and web-enabled online surveys. It will incorporate a 1-800 message, fax and e-mail options for participant convenience, and use postage-paid reply mail service, address forwarding, and multiple efforts in multiple formats to locate patients whose addresses, phone numbers or e-mail become insufficient. Participants will be provided online accounts to complete required surveys. Our centralized data collection center will not have access to randomization assignments in order to minimize bias in data collection. An outcomes assessment committee will blindly review all adverse event reports. Despite rigorous efforts to minimize missing data or outcome information, inevitably there will be some patients with missing outcome information. We will use the methods described above to mitigate biases due to missing data, or to assess the sensitivity of our results to assumptions about missing data.

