### Data Management

At monthly intervals Statix, the central data collection agent, will transfer form files electronically to the Data Coordinating Center at the University of Maryland. The Data Coordinating Center will archive those form files, edit them for completeness of forms and data items, edit them for within-form and across-form logical consistency of data items, and report on the edits to the Clinical Coordinating Center at MUSC. Statix will work with the Data Coordinating Center and the Clinical Coordinating Center to achieve complete form submission and correct errors in data items submitted. Delinquent forms and data item corrections will be submitted through the Data Coordinating Center in a process of continual form file updating. The Data Coordinating Center will convert the form files into data analysis files. The biostatistician in the Data Coordinating Center at the University of Maryland, Baltimore, will analyze those data files in consultation with the Executive Oversight Committee for preparation of reports to the Data and Safety Monitoring Board (DSMB) every six months.

There will be no outcome or endpoint data exchange between clinical sites other than the sharing of enrollment figures and progress towards enrollment goals at each site. This information will be made available in a secure section of the clinical trial website that is password protected and available only to clinical sites and their staff.

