## 5. RESEARCH TEAM AND ENVIRONMENT

The research team is comprised of investigators with complementary skills and perspectives. Drs. [name], [name], and [name] have worked together planning this project at the U of Maryland since 2009; in April, 2013, [name] relocated to MUSC. The group has extensive expertise in content (orthopaedic surgery/VTE research) and conduct (clinical trials, epidemiology) domains of the project.

The 16 member **Steering Committee**, chaired by the PI, is the governing body for the project and will meet in person on a quarterly basis to dispatch issues that require decision. Urgent matters will be addressed by conference call. The SC will oversee protocol refinement prior to implementation, and monitor patient enrollment, individual site performance, milestone accomplishment, and work of the committees and coordinating centers.

The **Clinical Coordinating Center (CCC)** will be based at the Medical University of South Carolina and directed by [name]. The CCC will be responsible for organization of the clinical trial sites, organization of the central IRB residing at MUSC, monitoring of enrollment and overall site performance, reconciliation and payment of all invoices related to the trial, orchestration and arrangement of meetings of site investigators, preparation and submission of regular progress reports to PCORI, and oversight of data analysis and preparation of manuscripts related to the trial.

The **Data Coordinating Center (DCC)** will be responsible for receipt and organization of data files from Statix, cleaning and editing of those files for analysis, merging randomization and data files to create unblinded files in support of preparation of reports to the DSMB and the Executive Oversight Committee.

The **Patient Advisory Board (PAB)** consists of up to 5 THA and 5 TKA patients (5 men/5 women), two representatives of national patient advocacy groups (National Blood Clot Alliance and North American Thrombosis Forum Patient Advocacy Committee), and a physician expert in study of patient preferences ([name]). The group is racially and socioeconomically diverse.

The **Outcomes Assessment Committee (OAC)** will review and validate outcomes on an ongoing basis during the course of the trial and adjudicate adverse events based on blinded site reports.

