A **Data and Safety Monitoring Board (DSMB)** will be formed in accordance with provisions for protection of human research subjects according to MUSC and PCORI guidelines. It will meet twice yearly, or as directed by the SC, OAC, and PCORI staff.

The **Executive Oversight Committee** will oversee operational details and ongoing timelines for efficient progress of the study.

**Statix** is a centralized data collection agency based in Salt Lake City, UT. Statix will serve as the primary centralized data collection agent as well as the randomization agent for the trial.

**CTRIC** is a research data processing agency based in Baltimore, MD and will assist in data processing and creation of orderly report formats for the DSMB.

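### An operational committee is given unblinded data while the trial runs, with no stated purpose or limit

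*Protocol*

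**What the plan says.** **Executive Oversight Committee.** Three places in the Protocol bear on its access:
- Confidentiality Risks (4.1.3) states that "the executive oversight committee will have access to unblinded data", alongside the Data Coordinating Center.
- Section 5 gives the Data Coordinating Center the task of "merging randomization and data files to create unblinded files in support of preparation of reports to the DSMB and the Executive Oversight Committee".
- Data Management (3.1.3) says that the biostatistician "will analyze those data files in consultation with the Executive Oversight Committee" to prepare the six-monthly DSMB reports.

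Section 5 describes this committee in one sentence: it "will oversee operational details and ongoing timelines for efficient progress of the study". Its membership is not given. The governing body is the Steering Committee.

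**Safeguards on results by arm.** Confidentiality Risks also says: "Only results for the entire study population (without regard to treatment group) will be presented during open sessions of the DSMB". Closed-session reports carry Group A, B or C labels in case someone outside the session sees them, and access to data is limited to those who need it.

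**Central data collector.** Missing Data (3.1.3) says: "Our centralized data collection center will not have access to randomization assignments in order to minimize bias in data collection". Section 5 says: "Statix will serve as the primary centralized data collection agent as well as the randomization agent for the trial". The paragraph on recruitment and randomisation after Table 1 says that the same firm provides the randomisation program, and 3.1.2 f) has it make the follow-up contacts.

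**The concern.** The trial is open-label, and 3.1.3 itself names this as a threat to unbiased comparison. Individual patients' assignments are known locally, so the confidentiality that can still be protected is that of accumulating outcomes compared by arm. Those who shape the conduct of the trial should not see them, because such knowledge can influence decisions on arms, allocation, sample size and closure of recruitment.

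Such decisions were made here. Warfarin was removed in 2023, allocation became 1:1, and the power for aspirin against warfarin in Table 1 was worked out from numbers randomised as of May 1, 2023. If an operational committee could see outcomes by arm at that time, the trial loses its simplest evidence that the decisions were independent of those outcomes.

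The data-collector statement raises a smaller question. It is offered as a protection against bias, but the firm it describes also runs the randomisation, and no internal separation is set out.

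**Working it through.** No figure in the plan is at issue, so the check is a comparison of the text.

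**1. Is the access during the trial or only at its end?** During it. Data Management ties the consultation to the six-monthly DSMB reports, and section 5 names the committee as a recipient of reports built from unblinded files.

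**2. What could be seen?** The unblinded files are made by joining randomisation data to outcome data. Section 4.5 puts outcome information in the six-monthly reports and plans interim monitoring of the primary outcome. The Protocol does not say what the committee's own reports contain, and nothing limits them to pooled figures.

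**3. How often?** Section 3.1 gives 97 months of enrolment and 6 months of trailing follow-up. With a report every 6 months:
- enrolment only: 97 / 6 = 16.2, about 16 occasions;
- with trailing follow-up: (97 + 6) / 6 = 103 / 6 = 17.2, about 17 occasions.

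This assumes access at every report, which the Protocol implies but does not state.

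**4. Is a need stated?** The only function beyond operations is in 4.1.3, where the DSMB and an executive oversight group determine which SAEs go to the IRB. That supports access to individual SAE information. It does not require comparative outcomes by arm.

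**5. Do the safeguards still work?** Pooled open sessions and coded labels serve to keep arm-level results within the closed session. A second route to the same data, through the Executive Oversight Committee, bypasses both. Need-to-know access cannot be checked where no need is stated.

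**6. Central data collector.** The statement in Missing Data and the dual role in section 5 can both be true only if the firm separates its randomisation function from its follow-up staff. The Protocol does not describe that separation. It does have the Data Coordinating Center merge randomisation and data files, which suggests that the two are held apart until then. The texts are in tension; a failure is not shown.

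**The case against.** The strongest reply is that the access is disclosed openly and breaks no promise. No section says that this committee is masked, and none of the bias protections listed in 3.1.3 (independent central contact, redaction, blinded classification) concerns it. That stands: the access weakens the confidentiality rules but does not breach a stated blind. The SAE role is also real and should be kept.

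A reader might infer more, in four ways that the document does not support:
- **That the 2023 changes were driven by outcomes.** Section 3.1.2 gives a logistical reason for removing warfarin (barriers to home health and INR testing) and records the funder's approval. Section 4.5 gives the DSMB a role in approving amendments.
- **That the committee runs the trial.** The Steering Committee governs, and the membership of the Executive Oversight Committee is unstated.
- **That the collector's blinding does not exist.** Missing Data states the restriction itself, and one firm can hold both roles with separated access.
- **That callers learn the arm before asking about events.** Section 3.1.3 mentions "the follow-up contact to ascertain treatment" but not who asks or in what order. The topics listed for central personnel in 3.1.2 f) do not include medication.

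The effect on endpoints is also bounded. The Outcomes Assessment Committee adjudicates without knowing the group. Events are also found through audit at discharge, discovery by coordinators, record review of 6-month non-responders and the National Death Index.

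**Conclusion.** The point holds for the Executive Oversight Committee. Three places give a committee described as operational access to unblinded data during the trial, with no purpose or limit stated, against safeguards in the same subsection that aim at the opposite. The size of any bias cannot be derived from the document. The exposure is about 16 to 17 reporting occasions if access comes with each six-monthly report. What is lost is the ability to demonstrate that design decisions were independent of results by arm; there is no evidence that independence was in fact lost.

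The data-collector point is secondary and calls for clarification. Blinded endpoint adjudication is untouched. The conclusion assumes that unblinded means linked to treatment group, as the description of the merged files indicates, and that no document outside the Protocol already restricts the committee's reports.

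**What to change.** 1. Amend Data Management, Confidentiality Risks and the Data Coordinating Center paragraph in section 5 so that comparative arm-level interim data go only to the DSMB and the unblinded Data Coordinating Center statisticians. The Executive Oversight Committee receives pooled data, plus individual SAE information as needed for its part in IRB reporting.
2. Record by role who had arm-level access before the 2023 changes, so that the independence of those decisions can be assessed.
3. In Missing Data and section 5, either state the role-based separation within the firm between randomisation and follow-up staff, or withdraw the claim that the collection centre has no access to assignments.

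The cost is wording, a change in report distribution and one retrospective record. The downside is that the committee loses sight of interim results by arm. Moving custody of the allocation list is not needed and would be disruptive in a running trial: Table 1 shows 5,132 + 5,389 = 10,521 patients randomised to aspirin or warfarin alone by May 1, 2023.
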